11.3.2 Overall Treatment Evaluation

The 15-graded OTE responses will be broken down into categories as follows:

Table 4 OTE responses and collapsed categories

OTE responses, Improvement/deterioration	Collapsed categories
A very great deal better	Large improvement
A great deal better	
A good deal better	Moderate improvement
Moderately better	
Somewhat better	Small improvement
A little better	
Almost the same, hardly better at all	Unchanged
About the same	
Almost the same, hardly worse at all	
A little worse	Deteriorated
Somewhat worse	
Moderately worse	
A good deal worse	
A great deal worse	
A very great deal worse	

11.4 Calculation or derivation of pharmacokinetic variables

The PK analyses will be performed at AstraZeneca R&D. Population mean and variability parameters will be estimated for oral total plasma clearance (CL/F), which determines total drug exposure, AUC, and for other pharmacokinetic parameters as applicable.

12. STATISTICAL METHODS AND SAMPLE SIZE DETERMINATION BY ASTRAZENECA

12.1 Description of analysis sets

12.1.1 Efficacy analysis set

All randomized patients, who receive at least one dose of IP, will be included in the Full Analysis Set (FAS). The FAS data will be analysed as randomized ie, in as-randomized analyses patients are analysed based on their randomized treatment. Randomized treatment is defined as the treatment associated with the randomization code given to the patient, identified via the randomization schedule.

12.1.2 Safety analysis set

All patients who received at least one dose of IP and for whom any post-dose data are available will be included in the safety population. Throughout the safety results sections, erroneously treated patients (eg, those randomized to treatment A but actually given treatment B) will be accounted for in the actual treatment group. The data of safety analysis set will be analysed as treated.

12.2 Methods of statistical analyses

12.2.1 Statistical evaluation – general aspects

The FAS will be used in the efficacy analyses described in this section. Analyses on RESQ-eD data will be based on imputed data. Unless otherwise stated, daily (approximately a 24 h period) values will be used. All patient reported outcome analyses will be calculated by using pooled data from all languages and cultures, if nothing else is stated under each paragraph. A Statistical analysis plan (SAP) will be prepared before unblinding data.

In the event of a dose group being terminated due to safety stopping criteria, the dose group would be excluded from the primary efficacy analyses comparing AZD3355 to placebo but included in safety presentations, PK analyses and the estimations of dose-response curves.

The statistical analysis will be performed by Statistics and Informatics, AstraZeneca R&D Mölndal, using mainly SAS® version 8.2. If available and necessary SAS® version 9.0 will be used.

12.2.2 Primary objective

The primary objective, to evaluate the effect of four doses of AZD3355 compared to placebo using the responder definition, will be evaluated by pairwise comparisons. Each dose level will be compared to placebo using logistic regression with dose as a factor variable. Based on experience from previous studies ([D9120C00011](#) and [D9120C00027](#)), the symptom frequency during baseline is expected to be associated with the response variable. Therefore, the proportion of days of not more than mild symptoms during baseline will be included as a covariate. The tests will be one-sided with a significance level of 10%. The multiplicity issue will be handled by using a step down procedure where AZD3355 is tested sequentially

starting with the highest dose. If the null hypothesis of no difference between AZD3355 240 mg and placebo is not rejected no further dose level will be tested. If the null hypothesis is rejected, AZD3355 240 mg is demonstrated to have an effect and AZD3355 180 mg will be tested compared to placebo. If the null hypothesis of no difference between AZD3355 180 mg and placebo is not rejected, no further dose level is tested. If the null hypothesis is rejected, AZD3355 180 mg is demonstrated to have effect and AZD3355 120 mg will be tested versus placebo.

Estimates and two-sided 95% confidence intervals of the odds ratios of each dose level compared to placebo will be calculated.

An additional explorative logistic regression with additional covariates will be fitted to the data. Details of this analysis will be presented in the SAP.

In addition, the proportion of responders per treatment will be presented.

Since the number of patients at each centre is expected to be few, the country-treatment interaction will be evaluated instead of centre-treatment interaction. A Breslow-Day's test (two-sided with a significance level of 10%) will be used to evaluate the country-treatment interactions for the primary variable.

12.2.3 Secondary objectives

12.2.3.1 Alternative responder definition

As in the primary objective, the pairwise comparisons to placebo will be evaluated, but this time using the alternative responder definition. The secondary analysis will not be adjusted for multiplicity, hence the interpretation of these results should be made with caution of the multiplicity issue.

Estimates and two-sided 95% confidence intervals of the odds ratios of each dose level compared to placebo will be calculated.

12.2.3.2 Change in the proportion of days of not more than mild symptoms compared to baseline

The change from baseline to the treatment period in the proportion of days of not more than mild symptoms, both on the Overall symptoms domain in the RESQ-eD as well as for each domain separately will be analysed assuming data follows approximately a normal distribution. If the latter criteria is not fulfilled an appropriate transformation of the variable will be performed. Each dose level will be compared to placebo using an ANCOVA, where the baseline is included as a covariate. The results of the ANCOVA will be presented as estimates and two-sided 95% confidence intervals.

12.2.3.3 Dose response curves

Two versions of the dose response curve will be estimated, one based on the primary variable and one based on the change in the proportion of days of not more than mild symptoms

compared to baseline on the Overall symptoms domain in the RESQ-eD. The dose response curve for the primary variable will be estimated by a logistic regression model where dose is included as a continuous variable. The dose response curve for the change in proportion of days of not more than mild symptoms will be estimated using a 4-parameter E-max model. The main focus will be on the E-max model, and the logistic regression will be regarded as a supportive model. A more detailed description of the estimation of the dose response curves will be described in the SAP.

12.2.3.4 Efficacy over time

The proportion of patients with not more than mild symptoms by day will be presented graphically.

12.2.3.5 Internal consistency

The internal consistency of RESQ-eD domains will be evaluated by using Cronbach's alpha (Cronbach 1951). Cronbach's alpha will be estimated as

$$\alpha_c = \frac{m}{m-1} \left(1 - \frac{\sum \text{Var}(x_i)}{\text{Var}(\sum x_i)} \right)$$

where m is the number of items in the domain, $\text{Var}(x_i)$ is the estimated variance of the i^{th} item and the summation is over all items within a domain. Ninety-five % confidence intervals for the Cronbach's alpha coefficients will be presented. An alpha coefficient ≥ 0.70 will be interpreted as sufficient (Fayers et al 2007) to suggest that the items within a domain measure the same construct.

Cronbach's alpha will be calculated for each separate domain with more than one item, using the variable "item intensity over baseline".

If possible, Cronbach's alpha will be calculated with a subpopulation defined by the same languages version of the RESQ-eD. This will be done only for the subpopulation which is large enough to provide a reliable result.

Assuming the coefficient is 0.8 for a domain with 5 items, with 74 patients - or for a domain with 3 items, with 89 patients - the length of a 95% confidence interval for Cronbach's alpha is approximately ± 0.07 . The calculations are based on formulas given in Bonett 2002.

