2.2 Secondary objectives

The secondary objectives of the study are:

- To evaluate the effect on GERD symptoms of four doses of AZD3355 (60 mg, 120 mg, 180 mg and 240 mg bid) compared to placebo, as add-on treatment to a PPI by using an alternative responder definition; ie, at least 5 days of not more than mild GERD symptoms on average per week during the whole treatment period based on the Overall symptoms domain in the RESQ-eD
- To evaluate the effect on GERD symptoms of four doses of AZD3355 (60 mg, 120 mg, 180 mg and 240 mg bid) compared to placebo, as add-on treatment to a PPI by analysing the change in the proportion of days of not more than mild GERD symptoms compared to baseline, based on the Overall symptoms domain and for

each separate domain (Heartburn; Regurgitation; Hoarseness, cough and difficulty swallowing; Burping) in the RESQ-eD

- To evaluate the dose-response curve with respect to:
 - The responder definition
 - The change in the proportion of days of not more than mild GERD symptoms compared to baseline, based on the Overall symptoms domain in the RESQ-eD
- To assess basic measurement properties of the RESQ-eD
- To assess the pharmacokinetics of AZD3355 by population PK analyses with special regard to variability in the patient population
- To study the relationship between systemic exposure and response with special regard to the responder definition
- To study the prevalence of mucosal breaks in the target population through endoscopy at baseline during the study or historical reports
- To describe the endoscopic findings after the study treatment period, in patients with baseline endoscopy showing mucosal breaks.

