11.3 Calculation or derivation of patient reported outcome variables

11.3.1 Reflux Symptom Questionnaire e-diary

The RESQ-eD consists of 13 items that combine into an Overall symptoms domain and 4 separate domains:

- Heartburn
 - burning feeling behind the breastbone
 - pain behind the breastbone
 - heartburn
 - burning feeling in centre of the upper stomach
 - pain in centre of the upper stomach
- Regurgitation
 - acid taste in the mouth
 - bitter taste in the mouth
 - unpleasant movement of material upwards from the stomach
 - stomach contents (liquid or food) moving upwards to your throat and mouth
- Hoarseness, cough and difficulty swallowing
 - hoarseness
 - cough
 - difficulty swallowing
- Burping
 - Burping.

The e-diary ratings of the 6-graded Likert scale are transformed to numerical values, from “Did not have” = 0 to “Severe” = 5.

When imputing missing values, morning registrations will be regarded as one sequence of observations and evening registrations as another sequence of observations. Missing values in the sequence of morning or evening registrations respectively will be imputed according to the following rules. If a single observation is missing, the missing value will be replaced by the larger of the two surrounding values. If two or more consecutive observations are missing the values will remain missing.

Values of intensity for a day (approximately a 24 h period) will then be constructed using the imputed sequences of evening and morning registrations of item intensities. A day will consist of an evening and the following morning registration. The daily item intensity will be defined as the maximum of the two registrations. If either the morning or the evening registration is missing, the corresponding daily value will be set to missing in the statistical analyses. In the algorithm determining whether a patient is eligible for randomization missing values are not imputed, and the daily value will be the maximum value of the evening and morning registration even if one of them is missing.

The domain intensity on a given day will be derived as the mean daily intensities of the items that form the domain.

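### A Cronbach's alpha of 0.70 or more shows adequate internal consistency; it cannot show that the items of a domain measure one construct rather than two moderately correlated ones

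*Protocol*

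**What the plan says.** One secondary objective (section 2.2) reads "To assess basic measurement properties of the RESQ-eD". Section 12.2.3.5 carries it out with Cronbach's alpha, which "will be calculated for each separate domain with more than one item" from each patient's mean item intensities over the seven baseline days. That covers Heartburn (five items), Regurgitation (four) and the hoarseness, cough and swallowing domain (three). A value of 0.70 or more "will be interpreted as sufficient (Fayers et al 2007) to suggest that the items within a domain measure the same construct". The section adds that "Ninety-five % confidence intervals for the Cronbach's alpha coefficients will be presented", but the interval plays no part in the rule. It closes with a precision statement: "Assuming the coefficient is 0.8 for a domain with 5 items, with 74 patients", "or for a domain with 3 items, with 89 patients", the interval is about ±0.07.

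Section 11.3.1 lists the items. Heartburn joins three breastbone or heartburn items with two upper-stomach items, one of them "burning feeling in centre of the upper stomach". Regurgitation joins two taste items with two items on material moving upwards. Sections 1.3, 3.2 and 6.5.1 attribute the domain structure and the validity of the diary to the earlier validation study, D9120C00027, on which this trial is to build.

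**The concern.** The rule draws a conclusion about dimensionality from a reliability coefficient. Alpha describes how consistently a set of items measures something, given that they share a construct. It does not test whether they share one. A domain that mixed two related symptoms could pass, and the report would then say that its items appear to measure the same thing. The item lists make this conceivable, because two of the domains contain items that differ in body site or in type of sensation.

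At stake is what a pass adds to the evidence on the diary. The domain score is the mean of its items (section 11.3.1) and is carried into the test-retest and effect-size analyses (sections 12.2.3.6 and 12.2.3.7). A reader told that the domain is one construct will read those summaries as describing one symptom.

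**Working it through.** **The plan's own figure.** Bonett's sample-size formula is n = [8k/(k−1)] × [1.96 / ln((1−L)/(1−U))]² + 2. With alpha 0.8 ± 0.07, L = 0.73 and U = 0.87.

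- k = 5: n = 73.9, rounded up to 74.
- k = 3: n = 88.3, rounded up to 89.

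Both agree with the protocol. The interval at those sizes is 0.71 to 0.86. The precision statement is sound, but it concerns how well alpha is estimated, not what alpha means.

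**What alpha depends on.** For standardised items the formula in section 12.2.3.5 becomes alpha = k/(k−1) × (1 − k/S), where S is the sum of all entries of the item correlation matrix. The arrangement of the correlations drops out. Alpha reaches 0.70 at a mean inter-item correlation of 0.7/(5 − 4×0.7) = 0.32 for five items, and 0.7/(4 − 3×0.7) = 0.37 for four.

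**Same alpha, different structure (five items).**

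- One construct, every correlation 0.44: S = 5 + 20×0.44 = 13.8.
- Two constructs, 3+2 items, 0.8 within and 0.2 between: S = 5 + 8×0.8 + 12×0.2 = 13.8.

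Both give alpha = 1.25 × (1 − 5/13.8) = 0.80. The rule cannot separate them.

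**How often a two-construct domain would pass.** Inputs from the protocol: k = 5 and k = 4, threshold 0.70, about 650 patients. Assumed, because the protocol gives no values: the 3+2 and 2+2 splits, the item correlation rw within a construct, and the correlation φ between the two constructs (so items from different constructs correlate at φ×rw). Multivariate normal samples of 650 were simulated and alpha computed in each. For rw = 0.7:

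| φ | Heartburn alpha | Heartburn passes | Regurgitation alpha | Regurgitation passes |
|---|---|---|---|---|
| 0 | 0.66 | 3% | 0.55 | 0% |
| 0.2 | 0.74 | 99% | 0.66 | 3% |
| 0.3 | 0.77 | 100% | 0.70 | about 60% |
| 0.4 | 0.80 | 100% | 0.74 | 98–99% |
| 0.5 | 0.83 | 100% | 0.78 | 100% |

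At φ = 0.5 the Heartburn correlation matrix still has a second eigenvalue of 1.12.

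**Sensitivity to the assumptions.** With unrelated constructs (φ = 0), Heartburn passes in about 3%, 50% and 97% of samples at rw = 0.7, 0.8 and 0.9. Regurgitation passes in under 1% even at rw = 0.9. The φ at which population alpha equals 0.70 is:

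| rw | Heartburn | Regurgitation |
|---|---|---|
| 0.5 | 0.39 | 0.61 |
| 0.6 | 0.22 | 0.42 |
| 0.7 | 0.09 | 0.29 |
| 0.8 | about 0 | 0.19 |

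In a language subgroup of 74 to 89 patients the outcome is less certain near the threshold. Regurgitation at rw = 0.7 and φ = 0.4 passes in 77 to 79% of samples.

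**The case against.** The strongest reply is that this is one cautious clause in a secondary psychometric analysis. The plan says that the value suggests a common construct, not that it proves one; the section is about internal consistency; and confidence intervals are shown. No analysis is made conditional on alpha. The domains were not derived here but come from the validation study, whose dimensionality evidence cannot be seen from the protocol. Factor models could also sit in the SAP, which is not at hand.

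Most of this stands, and it limits the point. Nothing is made here of the absence of a factor analysis. What remains is the interpretation that the protocol itself fixes, which calls the value sufficient. An extra analysis elsewhere would leave that sentence saying more than alpha can carry. The interval does not help either, because it expresses sampling error only.

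Three stronger readings might be inferred, and none is supported. First, that the domains would be confirmed almost whatever the data: the pass rate depends heavily on φ and rw, and unrelated constructs would usually be caught, above all in Regurgitation. Second, that the domain efficacy results are undermined: they are analysed unconditionally (section 12.2.3.2), and the variable counts days on which no item in the domain exceeds mild (section 11.3.1), a calculation that needs no single construct. Third, that alpha is the only support for the domains: the protocol attributes them to the earlier study.

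**Conclusion.** The point holds in a limited form, as a minor improvement. As written, the rule can lead to an unsupported secondary conclusion when a domain contains two moderately correlated constructs whose items are fairly strongly correlated. At 650 patients and rw = 0.7, that begins at a construct correlation of about 0.2 for Heartburn and between 0.3 and 0.4 for Regurgitation. That alpha cannot tell the two structures apart follows from its formula and needs no assumption. The pass rates do rest on assumed splits and correlations, and say nothing about which structure the diary actually has. The primary responder endpoint and the calculation of the separate-domain efficacy variables are unaffected.

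**What to change.** In section 12.2.3.5, keep alpha with its 95% confidence interval and say that 0.70 or more indicates adequate internal consistency only. Rest any statement that the items of a domain share a construct on one of two sources.

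- The baseline item data already collected: tabulate the inter-item correlations and check the fit of a one-factor model for Heartburn and for Regurgitation, against fit criteria stated in advance. The model has k(k+1)/2 − 2k degrees of freedom: 15 − 10 = 5 for Heartburn, 10 − 8 = 2 for Regurgitation, and 6 − 6 = 0 for the three-item domain. The last therefore cannot be tested this way, and its three pairwise correlations should be reported instead.
- Dimensionality evidence from the validation study, cited explicitly, if it exists.

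Checking one-factor fit also avoids relying on a two-factor model with only two items on a factor, which is poorly identified when the factors are nearly uncorrelated.

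The cost is a change of wording and, under the first option, one small extra analysis; no new patients, visits or data are needed. The drawback is that the domains may look less clean than alpha alone would suggest.

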12.2.3.6 Test-retest reliability

Test-retest reliability of the RESQ-eD will be investigated using Intraclass Correlation Coefficients (ICC), using patients in a stable condition between the randomization visit (visit 2) and the visit after 2 weeks treatment with IP (visit 4). A stable patient will be defined as a patient who scored "About the same", "Almost the same, hardly worse at all" or "Almost the same, hardly better at all" on the OTE after 2 weeks treatment.

Test-retest reliability will be calculated using the variables “domain intensity over baseline” and “domain intensity over the seven days prior to visit 4”, for each separate domain.

The test-retest reliability intraclass correlation coefficient (R) will be estimated as:

$$\hat{R} = \frac{BMS - WMS}{BMS + (k_0 - 1)WMS}$$

where BMS and WMS are the mean square values between-patients and within-patients respectively, and k_0 denotes the number of replicates per patient (two in this case).

A 95% confidence interval for R will be estimated as

$$R \leq \frac{\frac{BMS}{WMS} - F_{N-1, K-N, \alpha/2}}{\frac{BMS}{WMS} + (2-1)F_{N-1, K-N, \alpha/2}}, \quad R \geq \frac{\frac{BMS}{WMS} - F_{N-1, K-N, 1-\alpha/2}}{\frac{BMS}{WMS} + (2-1)F_{N-1, K-N, 1-\alpha/2}}$$

where N = number of patients, K = number of measurements and $\alpha = 0.05$.

The within-patient and between-patient mean square will be calculated by two-way analysis of variance (ANOVA) with the factors of patient and visit.

Patients with a missing value for either domain intensity over baseline or domain intensity over the seven days prior to visit 4 will be excluded from the test-retest calculations.

Intraclass correlation coefficients < 0.4 will be considered to represent poor reliability, values > 0.75 excellent reliability, and values in between fair to good reliability (Fleiss 1986).

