4.1 Inclusion criteria

For inclusion in the study patients should fulfil the following criteria:

1. Provision of informed consent prior to any study specific procedures
2. Male or female. Females of childbearing potential must be using a highly effective contraceptive method for at least the previous 3 months, see Section [5.1.1](#)
3. Age 18-70 years, inclusive
4. Body Mass Index (BMI) 18.5 – 35.0 kg/m², inclusive
5. Have at least 6 months history of GERD symptoms (need not to be consecutive)
6. Continuously treated during the last 4 weeks before enrolment with daily optimized unchanged PPI therapy with doses according to the country label, or regional where applicable, for any GERD indication. Patients with endoscopy verified reflux esophagitis (Los Angeles classification grade A-D) within the last 8 weeks must have completed the prescribed 8 weeks treatment with a PPI. An optimized PPI treatment is a treatment which according to the investigator judgment can not be further improved by changing brand or dosing of the PPI.

7. Have a PPI prescription with refills that cover the whole study period or instructions by a physician to use an over the counter (OTC) PPI in accordance with the labelling of their prescription counter-part
8. Able to read and write in the local language and use the e-diary device
9. **To be eligible for the screening phase** the patients must have reported in the RESQ-7 using 7 days recall of symptoms, a minimum of 3 days and a rating of at least moderate intensity on at least one of the following items; a burning feeling behind the breastbone or unpleasant movement of material upwards from the stomach. (An algorithm which is programmed in the e-diary device, will determine eligibility automatically).
10. **To be eligible for randomization** the patients must have recorded in the RESQ-eD on the last 7 days before randomization, a minimum of 3 days with a symptom intensity of at least moderate on either item, or any combination of both items (eg 1 day on one item and 2 days on the other); a burning feeling behind the breastbone or unpleasant movement of material upwards from the stomach. (An algorithm, which is programmed in the e-diary device, based on the e-diary recordings, will determine whether the patient fulfils the criteria).
11. An upper gastrointestinal endoscopy is required before randomization provided that:
 - no endoscopy has been performed within the past 24 months

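### Section 12.2.3.6 pairs a one-way ICC formula and interval with mean squares from a two-way ANOVA; with the residual as WMS, a shift between visits would go unseen

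*Protocol*

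**What the plan says.** Section 12.2.3.6 of the protocol estimates test-retest reliability for each RESQ-eD domain. It compares domain intensity over the baseline week with domain intensity over the seven days before visit 4, in patients whose OTE answer at week 2 falls in one of the three central categories. The estimator is R = (BMS − WMS)/(BMS + (k₀ − 1)WMS), "where BMS and WMS are the mean square values between-patients and within-patients respectively", with k₀ = 2. The 95% interval uses F quantiles on N−1 and K−N degrees of freedom, "where N = number of patients, K = number of measurements and" α = 0.05. Patients lacking either value are excluded.

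On the source of the mean squares the section says: "The within-patient and between-patient mean square will be calculated by two-way analysis of variance (ANOVA) with the factors of patient and visit". On interpretation it says: "Intraclass correlation coefficients < 0.4 will be considered to represent poor reliability, values > 0.75 excellent reliability", with fair to good in between.

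**The concern.** The formula and the interval belong to a one-way layout, in which everything that varies within a patient, including a common change from one visit to the next, counts as within-patient variation. A two-way ANOVA with visit as a factor takes that common change out before the error term is formed. A programmer who follows the ANOVA sentence will most naturally use the residual as WMS. The result is then a consistency coefficient, presented through a formula and interval meant for something else.

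A common shift is plausible here. By Section 11.3.1 the baseline is the seven days before visit 2. By criterion 10 of Section 4.1 that week had to contain "a minimum of 3 days with a symptom intensity of at least moderate on either item" (burning behind the breastbone, or upward movement of stomach material). Some regression to the mean is therefore built in, and the retest week comes after study treatment has begun. If a shift occurs, the planned coefficient would not show it. Assessing the basic measurement properties of the diary is a secondary objective (Section 2.2).

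**Working it through.** The protocol states no ICC value, so there is no figure to reproduce.

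**1. Degrees of freedom.** K must be the total number of measurements, because K = 2 would make K−N negative. With complete pairs K = 2N, so K−N = N. A one-way ANOVA on patient has N−1 and N degrees of freedom, which matches the printed interval. A two-way ANOVA on patient and visit has N−1 (patient), 1 (visit) and N−1 (residual). The printed N fits visit and residual pooled, 1 + (N−1) = N; it does not fit the residual alone.

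**2. Expected mean squares.** Let the between-patient variance be s²b, the residual variance s²e, with s²b + s²e = 1, and let d be the mean shift between visits in units of the single-measurement SD.
- BMS = 2s²b + s²e
- Two-way residual = s²e, whatever the value of d
- One-way WMS = [visit SS + residual SS]/N = [(N·d²/2 + s²e) + (N−1)s²e]/N = s²e + d²/2

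With k₀ = 2 the printed formula is R = (BMS − WMS)/(BMS + WMS). For comparison, the agreement coefficient is s²b/(1 + d²/2).

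**3. Numbers.** Reliability and shift are assumptions. For reliability 0.78, BMS = 1.78 and the residual is 0.22. For 0.60, BMS = 1.60 and the residual is 0.40.

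| Reliability | d (SD) | R with residual | One-way WMS | R with one-way WMS | Agreement |
|---|---|---|---|---|---|
| 0.78 | 0 | 1.56/2.00 = 0.780 | 0.220 | 0.780 | 0.780 |
| 0.78 | 0.2 | 0.780 | 0.240 | 1.540/2.020 = 0.762 | 0.765 |
| 0.78 | 0.3 | 0.780 | 0.265 | 1.515/2.045 = 0.741 | 0.746 |
| 0.78 | 0.5 | 0.780 | 0.345 | 1.435/2.125 = 0.675 | 0.693 |
| 0.60 | 0.3 | 0.600 | 0.445 | 1.155/2.045 = 0.565 | 0.574 |
| 0.60 | 0.5 | 0.600 | 0.525 | 1.075/2.125 = 0.506 | 0.533 |

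**4. When the label changes.** From 0.78, the one-way value reaches 0.75 when WMS = 0.25 × 1.78/1.75 = 0.254, so d = √(2 × 0.034) ≈ 0.26 SD. From 0.60, it reaches 0.40 when WMS = 0.6 × 1.60/1.4 = 0.686, so d = √(2 × 0.286) ≈ 0.76 SD.

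**5. The interval.** The degrees of freedom alone barely matter. At BMS/WMS = 7 and N = 100 the interval is 0.6501 to 0.8245 with N, and 0.6497 to 0.8246 with N−1. The removed visit variance matters more. In a simulation (3000 runs per setting, reliability 0.75, N = 100), the printed interval with the residual as WMS covered the agreement coefficient in 94%, 89% and 62% of runs at shifts of 0, 0.3 and 0.5 SD. With one-way WMS it covered it in 94%, 95% and 94%.

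**The case against.** The strongest defence is that the section never calls WMS a residual. It calls it the within-patients mean square and prints K−N degrees of freedom. If visit and residual sums of squares are pooled over N degrees of freedom, formula and interval are consistent and nothing is overstated. This reading cannot be excluded. But the text does not state the pooling, and a visit factor would then serve no purpose.

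Second, overstatement needs a shift. The protocol gives none, and the restriction to patients who rate themselves essentially unchanged should limit it. That stands: the size of the effect is unknown.

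Third, regression from a selected baseline week and a real treatment effect are not faults of the diary. Removing a common shift can be defended, and a consistency ICC is a legitimate choice. That stands too, but the plan would have to name the coefficient as such.

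A reader might also infer that the 0.4 and 0.75 cut-offs hold only for a one-way ICC. Section 12.2.3.6 applies them to intraclass correlations in general and cites a textbook that is not at hand, so the documents do not support that.

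Finally, little depends on the result. Section 1.3 says an earlier study already found the diary valid, reliable and responsive, and this trial adds to that documentation.

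**Conclusion.** The mismatch stands: the formula and interval are one-way and the named ANOVA is two-way. A reader might infer that the plan is certain to overstate reliability; the text does not go that far. Overstatement requires both that WMS be taken as the two-way residual and that a systematic visit shift exist among OTE-stable patients.

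Over the assumed range (reliability 0.60 and 0.78, shifts of 0.2 to 0.5 SD), the residual version exceeds the one-way ICC by about 0.02 to 0.10 and the agreement coefficient by about 0.015 to 0.09. The label moves from excellent to fair to good only in the 0.78 example, which lies just above the cut-off, and not at 0.2 SD. At 0.60 it does not change within that range.

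Severity is minor. The effect is confined to a secondary measurement-property objective and does not enter the primary test (Section 12.2.2), the dose-response curves (12.2.3.3) or the sample size (12.3).

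**What to change.** Replace the ANOVA sentence in Section 12.2.3.6 so that BMS and WMS come from a one-way analysis of variance with patient as the only factor. Equivalently, state that visit and residual sums of squares are pooled over N degrees of freedom. Either matches the printed formula and interval. Report the mean difference between the two weeks beside the ICC, so that any shift is visible and can be interpreted.

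If a consistency coefficient is intended, keep the two-way ANOVA, name the coefficient as such, define WMS as the residual, and use N−1 and N−1 degrees of freedom.

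The cost is one sentence in the protocol, repeated in the SAP if it restates the method. No extra data are needed. With the one-way version the reported ICC may be slightly lower.
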